#### **3.5.1 Dose Escalation**

Up to 4 cohort dose levels of TFP will be studied: 1, 2, 5, and 10 mg/day for up to 21 days each, as tolerated. Cohort A will start at 1 mg/day, and the dose will escalate to 2 mg/day in Cohort B, 5 mg/day in Cohort C, and 10 mg/day in Cohort D. At the start of each cohort, 3 subjects will be enrolled, and an interim analysis (IA) for safety and tolerability will be

conducted after all 3 subjects have completed 21 days of treatment (See [Section 6 Study Design](#) for details). The 21-day time frame is based on the t1/2 from the healthy volunteer 5 mg single dose TFP study ([Midha, 1983](#)), showing that TFP's elimination t1/2 is approximately 12-14 hours. Therefore, steady state is reached approximately 3 days after initiating therapy, and 21 days of therapy provides at least 18 days of exposure at steady state (the 1 and 2 mg doses likely have shorter t1/2 and so steady state will be reached even sooner in the first 2 cohorts).

Whereas some FIH trials may use an enrollment restriction rule such that only two subjects are dosed at a time, this trial will not use such an enrollment restriction design. Please see [Section 2 Brief Summary of Research](#) for the supporting rationale.

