## 6 Study Design

### 6.1 General Design

This study is a multi-center, Phase I/II, dose escalation, open-label study to determine the safety of TFP in adult subjects with DBA and RBC-transfusion-dependence. A 3+3 dose escalation regimen will be used. The maximum time on study drug will be 21 days with a 1 week post-treatment follow-up period. It is expected that up to 24 subjects can be recruited and complete the study within 12-18 months. The dose escalation study design is shown in Figure 1:

- If 2 or more of the 6 subjects in Cohort B demonstrate toxicity  $\geq$  Grade 3, the study will be stopped, and 1 mg/day will be declared the MTD.
  - If  $< 2$  of the 6 subjects in Cohort B demonstrate toxicity  $\geq$  Grade 3 within 21 days of starting therapy, Cohort C will start.
3. Cohort C: Three subjects will receive TFP 5 mg PO daily.
- If there is no toxicity  $\geq$  Grade 3 at the end of the 21 days, Cohort D will start.
  - If 1/3 subjects in Cohort C demonstrates toxicity  $\geq$  Grade 3, an additional 3 subjects will be enrolled in Cohort C:
    - If 2 or more of the 6 subjects in Cohort C demonstrate toxicity  $\geq$  Grade 3, the study will be stopped, and 2 mg/day will be declared the MTD.
    - If  $< 2$  of the 6 subjects in Cohort C demonstrate toxicity  $\geq$  Grade 3 within 21 days of starting therapy, cohort D will start.
4. Cohort D: Three subjects will receive TFP 10 mg PO daily.
- If 0/3 subjects in Cohort D demonstrates toxicity  $\geq$  Grade 3, the study will be stopped, and 10 mg/day will be declared the MTD.
  - If 1/3 subjects in Cohort D demonstrates toxicity  $\geq$  Grade 3, an additional 3 subjects will be enrolled in Cohort D.
  - If 2 or more of the 6 subjects in Cohort D demonstrate toxicity  $\geq$  Grade 3, the study will be stopped, and 5 mg/day will be declared the MTD.
  - If  $< 2$  of the 6 subjects in Cohort D demonstrate toxicity  $\geq$  Grade 3 within 21 days of starting therapy, 10mg/day will be declared the MTD.

Each subject will undergo safety assessments as per the required schedule while on the study drug. All dosed subjects will be followed for an additional 1 week after discontinuing study drug (post-study safety follow-up). There will be no more than 6 subjects enrolled at any particular time.

Treatment will be discontinued for any subject if their Hb is > 12 gm/dL, not associated with RBC transfusions.

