## 7.2 Exclusion Criteria

Subjects who meet any of the following criteria will not be eligible to participate in the study:

1. Liver: aspartate aminotransferase (AST) > 5 x the upper limit of normal (ULN), alanine aminotransferase (ALT) >5 x ULN, or bilirubin > 5 x ULN.
2. Heart disease (New York Heart Association classification of  $\geq 3$ ; Appendix F).
3. History of angina.
4. Uncontrolled hypertension. If hypertension is considered clinically stable, systolic blood pressure must be <150 mmHg or diastolic blood pressure must be <100 mmHg.
5. Subjects currently responsive to corticosteroids for treatment of DBA.
6. Treatment with another investigational drug or device <56 days pre-study entry. Subjects who participated in an earlier cohort of this trial may participate in a subsequent cohort if (a) they meet all eligibility criteria, (b) did not experience any adverse effects  $\geq$  Grade 3 while on TFP, and (c) discontinued TFP  $\geq$  6 days (10 half-lives) prior to day 1 of the subsequent cohort.
7. Pregnant or lactating females.
8. Any history of severe allergic reaction requiring the use of epinephrine.
9. Known hypersensitivity to the study drug or other phenothiazines.
10. History or presence of extrapyramidal signs.
11. History of cancer.

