### **7.6.2 Data Collection and Follow-up for Withdrawn Subjects**

Subjects who discontinue from the Treatment Period early will still continue to the Follow-Up Period for 1 week from the last dose of TFP. For any subjects lost to follow-up, attempts will be made by phone to obtain permission to record at least survival data up to the end of study follow-up period.

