#### **9.5 Visit 4**

Visit 4 will be Day 29 ( $\pm 2$  days) of the study (Follow-up Period). The subject will undergo post-treatment safety assessment including a physical examination and blood work (CBC and chemistry panel). Transfusion history will be documented. The subject will be questioned and evaluated for any adverse events. This visit may be done virtually through a system that can visually assess the subject for neurologic issues. Blood work may be done at a local laboratory.

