#### ***Adverse Event Reporting Period***

All AEs will be recorded by the Investigator from the time the subject signs informed consent to 7 days after the last dose (completion of the 4th week). AEs and SAEs will be recorded on the AE page of the CRF and in the subject's source documents. All SAEs must be reported within 24 hours of the Investigator's knowledge of the event by facsimile, or other appropriate method, using the SAE Report Form, or approved equivalent form.

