#### **Description of procedure**

The study is 29 days long and consists of taking the study drug TFP for 21 days and being monitored for an additional 8 days. The patient will have a total of 4 visits over the period of 29 days. A review of the patient's history, physical examination, and laboratory blood work will be

done in order to determine if the patient is eligible to participate. While the patient is taking the TFP, he or she will need to be seen at The Feinstein Institutes for Medical Research or the participating institution 3 times over the first 21 days and virtually for the last visit. During the first 21 days the patient will be taking TFP once a day, orally as a tablet, and will continue the red blood cell transfusions as routinely scheduled, every 3-4 weeks.

The following are some of the basic inclusion and exclusion criteria for this pilot trial.

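### Re-entry at a higher dose (exclusion 6) is not tied to completion of the 1-week off-drug safety follow-up, and its toxicity bar covers only effects that occur on drug

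*Combined protocol and SAP*

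**What the plan says.** Section 7.2, exclusion 6, sets three conditions for re-entry: (a) all eligibility criteria are met; (b) no adverse effect of Grade 3 or higher occurred during treatment; (c) TFP stopped at least 6 days, described as 10 half-lives, before Day 1 of the new cohort. The wording that joins (b) and (c) is "Grade 3 while on TFP, and (c) discontinued TFP".

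Other sections set the safety observation period:

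- Section 15.1 records adverse events "from the time the subject signs informed consent to 7 days after the last dose".
- Section 6.1: "All dosed subjects will be followed for an additional 1 week after discontinuing study drug (post-study safety follow-up".
- Section 7.6.2: subjects who stop early "will still continue to the Follow-Up Period for 1 week from the last dose of TFP".
- Section 9.5: "Visit 4 will be Day 29", with a window of ± 2 days. It includes an examination, blood count and chemistry.
- Appendix G tells patients that the study involves "taking the study drug TFP for 21 days and being monitored for an additional 8 days".

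The next cohort can open before that period ends. Section 3.5.1 has the interim safety analysis "conducted after all 3 subjects have completed 21 days of treatment", and section 6.1 moves on from an expanded Cohort B if fewer than 2 of 6 subjects have toxicity "Grade 3 within 21 days of starting therapy, Cohort C will start". No section makes Visit 4 or the follow-up week a precondition of re-entry.

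**The concern.** Condition (b) is there to keep a subject who had a severe effect at one dose from receiving a higher one. It can do that only if it covers the period in which such effects are looked for, and that period runs a week past the last dose.

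Two gaps follow. First, a site can satisfy 6(c) and start the next dose level before the earlier course's 7-day window has closed, and possibly before Visit 4. Visit 4 would then no longer be an off-drug check of the lower dose. Second, a Grade 3 or higher event that starts in the off-drug week is outside the wording of 6(b). The boundary is also unclear at Visit 3, whose nominal Day 22 is the day after the last dose: whether a laboratory abnormality first found there occurred on drug is a matter of reading.

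At stake is the safety of a re-entering subject whose dose rises to 2 or 2.5 times its previous level, in a study whose primary objective is safety.

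**Working it through.** **1. The plan's own figure.** Section 3.5.1 gives a half-life of about 12 to 14 h. Washout in days = 10 × half-life / 24.

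- 12 h: 10 × 12 / 24 = 5.0 days.
- 14 h: 10 × 14 / 24 = 5.8 days.

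Both round up to the stated 6 days. Drug remaining after 6 days (144 h) is 0.5^(144/12) = 0.02% or 0.5^(144/14) = 0.08%. Carry-over is not the issue.

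**2. Calendar.** Dosing is on Days 1 to 21 (section 8.2).

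- Earliest re-entry: 21 + 6 = Day 27, or 22 + 6 = Day 28 if counted from the first dose-free day.
- End of the adverse event window: 21 + 7 = Day 28.
- Visit 4: 29 ± 2 = Days 27 to 31.
- Dose-free days before re-entry: Days 22 to 26 = 5 of 7, or Days 22 to 27 = 6 of 7.
- Days shared by the two courses' adverse event windows: Days 27 and 28 = 2, or Day 28 = 1.
- Higher-dose tablet-days before Visit 4 = Visit 4 day − re-entry day, not below 0. For re-entry on Day 27 this is 0, 2 or 4 with Visit 4 on Day 27, 29 or 31. For re-entry on Day 28 it is 0, 1 or 3.

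**3. Dose steps.** 2/1 = 2.0, 5/2 = 2.5, 10/5 = 2.0.

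**4. Is Day 27 reachable?** Section 9.2 asks for Visit 1 within 7 days of a transfusion, and section 10 has transfusions every 3 to 4 weeks. Assume a fixed interval I of 21 or 28 days and a first course that began k = 0 to 7 days after a transfusion (8 patterns). Days since the last transfusion on Day D = (D − 1 + k) mod I, which must be 7 or less.

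- I = 21: Day 27 qualifies for k = 0 to 2, so 3 of 8 patterns.
- I = 28: Day 27 qualifies for k = 2 to 7, so 6 of 8 patterns.

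So Day 27 is feasible for some subjects. How often the interim analysis would be finished and the next cohort open by then cannot be computed from the documents.

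**5. What other provisions leave uncovered in the off-drug week.**

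- Exclusions 9 and 10 bar hypersensitivity and any history of extrapyramidal signs.
- Section 15.4, Scenario 1, removes subjects with extrapyramidal symptoms, signs of tardive dyskinesia or NMS, and those with an SAE or treatment-emergent Grade 3 or higher event judged related to TFP. It sets no day limit.
- Section 7.6.1 lists any Grade 3 or higher toxicity as sufficient reason for withdrawal, but does not compel it.
- Exclusion 1 (AST, ALT or bilirubin above 5 × ULN) tests current values, so a recovered value passes. Section 10 calls severe cytopenia a bar, but 7.1 and 7.2 set no cell-count limit.

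The remainder is mainly a non-serious Grade 3 or higher event, such as a cytopenia or transaminase rise, that starts off drug, improves before the new Day 1, and is not handled under 15.4 as a related treatment-emergent event. The documents give no rate for it.

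**The case against.** The strongest reply is that nothing here is contradictory. Condition (c) is a minimum, labelled as pharmacokinetic, and does not cancel the follow-up duty in 6.1 and 7.6.2. Condition (a) brings back inclusion 9, agreement to the visit schedule and all protocol requirements. Read together, a careful site would finish the week first. This stands in part: a reader might infer that exclusion 6 conflicts with the follow-up rules, but a floor does not forbid waiting longer. What is missing is the link. Neither inclusion 9 nor the follow-up duty makes Visit 4 a condition of re-entry.

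Second, little observation is lost. Visit 1 of the new course repeats the examination and bloods before dosing, Visit 4 may be held on Day 27 before redosing, and adverse event recording would continue in the new course. This stands and limits the harm, though the off-drug week is still cut short.

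Third, 7.6.1 and 15.4 already reach severe off-drug events. This also stands in part: 7.6.1 is discretionary and 15.4 needs a causality judgment, whereas 6(b) needs neither. It does mean that one should not infer free re-entry after severe toxicity.

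Fourth, the floor binds mainly a cohort's last finishers, at no more than three cohort transitions. That is correct.

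**Conclusion.** The point holds as a minor to moderate correction of safety wording. Exclusion 6 allows redosing at 2 to 2.5 times the earlier dose from Day 27 or 28, which is 1 to 2 days inside the 7-day window and possibly before Visit 4. It also does not expressly bar a Grade 3 or higher event that first appears off drug. The day counts assume a full 21-day course.

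Two stronger readings are not supported. The washout is not too short for elimination. Nor does the gap distort the 3+3 decisions: the escalation text that can be read (Cohorts B to D) counts toxicity within 21 days of starting therapy, so an event after redosing on Days 27 or 28 counts toward the higher dose. What stays unclear is only which course such an event belongs to in the adverse event summary (14.2) and under 15.4, which gives no day window.

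**What to change.** Amend exclusion 6:

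- **6(b):** no adverse effect of Grade 3 or higher from the first dose through completion of Visit 4 of the earlier course, and for at least 7 days after its last dose. Ending at Day 28 alone would not be enough: Visit 4 has the only scheduled bloods after Visit 3 and can fall on Days 29 to 31.
- **6(c):** keep 6 days as the pharmacokinetic minimum, and add that the 7-day window must have closed and Visit 4 been completed, with its results reviewed, before Day 1 of the next cohort.
- Allow Visit 4 on Day 28, inside its window, for subjects who intend to re-enter.

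**Cost.** If Visit 4 results are reviewed by the next day, the earliest start moves from Day 27 to Day 29 (Visit 4 by Day 28), Day 30 (Visit 4 on Day 29) or Day 32 (Visit 4 on Day 31), a shift of 2 to 5 days. Adding the 7-day transfusion rule, on the assumptions of step 4:

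- *4-weekly transfusions.* A Day 29 start qualifies for all 8 patterns and costs 0 to 2 days. With Visit 4 on Day 29, 1 of 8 patterns must wait for the next transfusion (23 days). With Visit 4 on Day 31, 3 of 8 must (23 to 25 days).
- *3-weekly transfusions.* 5 of 8 patterns are unaffected, because they cannot start before Days 36 to 40 anyway. Another 2 of 8 wait 14 to 15 days, and 1 of 8 waits 2 days, or 16 if Visit 4 is after Day 28.

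A few re-entrants may be lost, which matters in a rare disease. Holding Visit 4 by Day 28 keeps that loss small.

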## 7.3 Vulnerable Populations

No vulnerable populations are specifically being targeted for this study.

- Children or viable neonate
- Cognitively impaired
- Pregnant Women, Fetuses or neonates of uncertain viability or nonviable
- Prisoners
- NSLIJ Employees, residents, fellows, etc
- poor/uninsured
- Students
- Minorities
- Elderly

## **7.4 Subject Recruitment and Screening**

[name], is the PI and the Director and [name], PhD is a Co-Investigator and the Co-Director of the Diamond Blackfan Anemia Registry of North America, respectively. The DBAR is housed at the Feinstein Institute for Medical Research. There are over 750 subjects with Diamond Blackfan anemia enrolled in this Registry. Because of this, the investigators have access to the specific subject population required for this study. Subjects contact the DBAR periodically to inquire about available studies. Also the DBA Foundation (DBAF) (the family group) has access to most of the DBA families. The DBAF is highly supportive of the research and they also encourage the families to contact the DBAR for any available studies. We have prepared a study announcement (Appendix G) to inform the subjects of the study as we have for other studies in the past. This will be posted on the DBAF website (mostly visited by subjects/families) and our DBAR website (often visited by physicians as well as subjects/families) and has worked well previously.

Once informed consent is obtained from the subject, the following screening requirements will be performed:

- 1- Physical examination (including height at 1st visit only, weight, vital signs, blood pressure and neurological examination)
- 2- Hematology evaluation including RBC count, hemoglobin, hematocrit, absolute reticulocyte count, white blood cell count, absolute neutrophil count, and platelet count
- 3- Blood chemistry including blood urea nitrogen, creatinine, bilirubin [total and direct], aspartate aminotransferase [AST], and alanine aminotransferase [ALT])
- 4- If female, serum pregnancy test
- 5- Documentation of transfusion history for > 3 months before initiation of treatment

## **7.5 Consent Process**

Informed consent will be obtained by the study PI or authorized co-investigators after they have fully explained the study. The study will be presented to all eligible subjects and explained in terms that are appropriate for each subject. After a full discussion and the

opportunity to ask questions, subjects will be consented. The subject may take as much time as needed to decide on his/her participation in the study, and may consent after the initial contact is made. The consent will be obtained either in the outpatient area at a regular office visit or via mail, after the study is discussed on a telephone call.

The subjects with DBA who may be eligible for this study may live in any state in the United States. Since travel may be difficult, it is often necessary to screen the subject for eligibility before they travel for the study. Therefore the consent is mailed to the subject. Once the subject has the consent in hand, the consent will be reviewed with him/her over the phone in its entirety. Questions can be asked and answered and the subject can determine the appropriateness of the study for him/herself. Once consent is signed and received by the PI, then the screening procedure can begin. Eligibility can therefore be determined prior to the subject's travel and confirmed upon subject's arrival to the office visit. A standard informed consent form will be utilized for this study. Subjects may have family members, their local physicians and any other chosen individuals review the consent with them prior to their signing. For subjects who sign consent remotely, the study PI or authorized co-investigator will review the study and the consent form again when the subject comes for the in-person physical examination and to begin the study. At that time an enrollment note will document the continued willingness of the subject to participate in the study.

The study is 4 weeks in duration and subjects may withdraw their consent at any time. Subjects will be seen weekly for the actual study drug timeframe of the study and will be given the opportunity to withdraw consent at any time.

This study does not involve subjects less than 18 years of age.

This study does not involve cognitively impaired adults.

Non-English speaking subjects with DBA are eligible for this study. Our institution provides a translator service through Pacific Interpreters, Inc. Any language can be accommodated. The translator will be used to explain the consent and give the subject an opportunity to ask questions and have them answered. The subject will be given a short form of the consent to sign.

## **7.6 Early Withdrawal of Subjects**

### **7.6.1 When and How to Withdraw Subjects**

The following reasons are considered sufficient for withdrawing a subject from the study drug and/or from the study:

- Sustained hemoglobin  $\geq$  12 mg/dL (not influenced by transfusions).
- Any toxicity  $\geq$  Grade 3 (Appendix H).
- Adverse event that, in the judgment of the investigator, may cause severe or permanent harm or that rules out continuation of treatment.
- Hypersensitivity reaction to TFP.
- Withdrawal of consent.
- Death.
- Lost to follow-up.
- Pattern of significant noncompliance.

The reason for subject withdrawal must be documented in the subject chart / source records.

### **7.6.2 Data Collection and Follow-up for Withdrawn Subjects**

Subjects who discontinue from the Treatment Period early will still continue to the Follow-Up Period for 1 week from the last dose of TFP. For any subjects lost to follow-up, attempts will be made by phone to obtain permission to record at least survival data up to the end of study follow-up period.

